6.2 Rituximab

Other names

IDEC-C2B8, Rituxan.

Classification

Monoclonal antibody.

Mode of action

This chimeric mouse/human anti-CD20 antibody binds human complement and causes lysis of B-cells. It has significant activity in assays for antibody dependent cellular cytotoxicity.

Storage and stability

Stored at 2-8^o C. Reconstituted antibody is stable for 24 hours upon refrigeration followed by 12 hours at room temperature.

Preparation

Diluted with normal saline to a concentration of 1 - 4 mg/mL. Shaking can cause aggregation and precipitation of the antibody and should be avoided.

Route of Administration: Intravenous

AVAILABILITY AND ACCOUNTABILITY

Rituximab is commercially available in 10 mL (100 mg) and 50 mL (500 mg) single-use vials at a concentration of 10 mg /mL. Use of rituximab is considered standard care for this indication, and will not be provided by Merck.

Incompatibilities

Do not mix or dilute rituximab with other drugs. No incompatibilities between rituximab and polyvinylchloride or polyethylene bags have been observed.

Side effects

1. Infusion related symptoms: Fevers, chills, rigors, hypotension, anaphylaxis or hypersensitivity reactions, arrhythmia, dyspnea, bronchospasm, angioedema. In rare cases, severe and fatal cardiopulmonary events, including hypoxia, pulmonary infiltrates, acute respiratory distress syndrome, myocardial infarction, and cardiogenic shock, have occurred (4-7/10,000 patients or 0.04-0.07%.) Nearly all fatal infusion-related events occurred in association with the first infusion. Patients with preexisting cardiac conditions, including arrhythmia and angina, have had recurrences of these cardiac events during rituximab infusions.
2. Gastrointestinal: Nausea, vomiting.
3. Hematologic: Leukopenia, anemia, thrombocytopenia. In clinical trials, NCI CTC Grade 3 and 4 cytopenias were reported in 48% of patients treated with rituximab; these include: lymphopenia (40%), neutropenia (6%), leukopenia (4%), anemia (3%), and thrombocytopenia (2%). The median duration of lymphopenia was 14 days (range, 1 to 588 days) and of neutropenia was 13 days (range, 2 to 116 days). A single occurrence of transient aplastic anemia (pure red cell aplasia) and two occurrences of hemolytic anemia following rituximab therapy were reported.

In addition, there have been a limited number of postmarketing reports of prolonged pancytopenia, marrow hypoplasia, and late onset neutropenia (defined as occurring 40 days after the last dose of rituximab) in patients with hematologic malignancies. In reported cases of late onset neutropenia (NCI-CTC Grade 3 and 4), the median duration of neutropenia was 10 days (range 3 to 148 days). Documented resolution of the neutropenia was described in approximately one-half of the reported cases; of those with documented recovery, approximately half received growth factor support. In the remaining cases, information on resolution was not provided. More than half of the reported cases of delayed onset neutropenia occurred in patients who had undergone a prior autologous bone marrow transplantation. In an adequately designed, controlled, clinical trial, the reported incidence of NCI-CTC Grade 3 and 4 neutropenia was higher in patients receiving rituximab in combination with fludarabine as compared to those receiving fludarabine alone (76% [39/51] vs. 39% [21/53]).³³

4. Dermatologic: Rash, pruritus, urticaria, and rarely severe mucocutaneous reactions.
5. Infectious: Reactivation of hepatitis B; reactivation of other viral infections or increased susceptibility to other infections. Hepatitis B virus (HBV) reactivation with fulminant hepatitis, hepatic failure, and death has been reported in some patients with hematologic malignancies treated with rituximab. The majority of patients received rituximab in combination with chemotherapy. The median time to the diagnosis of hepatitis was approximately four months after the initiation of rituximab and approximately one month after the last dose.
6. Renal and electrolyte: Renal toxicity has occurred in patients with high numbers of circulating malignant cells (>25,000/mm²) or high tumor burden who experience tumor lysis syndrome. Although rare, tumor

lysis syndrome has been reported in postmarketing studies and is characterized in patients with a high number of circulating malignant cells (>25,000 ul) by rapid reduction in tumor volume, renal insufficiency, hyperkalemia, hypocalcemia, hyperuricemia, and hyperphosphatemia

7. Other: Headache, asthenia. The following immune serious adverse events have been reported to occur rarely (<0.1%) in patients following completion of rituximab infusions: arthritis, disorders of blood vessels (vasculitis, serum sickness and lupus-like syndrome), lung disorders including pleuritis and scarring of the lung (bronchiolitis obliterans), eye disorders (uveitis and optic neuritis), and severe bullous skin reactions (including toxic epidermal necrolysis and pemphigus) that may result in fatal outcomes. Patients may have these symptoms alone or in combination with rash and polyarthritis. Five patients have developed deep vein thrombosis or pulmonary embolism as well. These were asymptomatic and found incidentally on CT scans.

Nursing implications

1. Monitor vital signs prior to Rituximab and if the patient has clinical deterioration during the infusion.
2. Have epinephrine for subcutaneous injections, diphenhydramine for intravenous injection, and resuscitation equipment for emergency management of anaphylactoid reactions available.
3. Monitor and alter infusion rates in the presence of toxicities.
4. Prolonged pancytopenia and bone marrow hypoplasia have been submitted as postmarketing reports. Patients should be monitored closely.
5. Prophylaxis for tumor lysis syndrome should be used in patients with high tumor burden, particularly with markedly elevated numbers of circulating malignant cells. Precautionary hospitalization should be made available for patients who experience severe infusion symptoms, which do not resolve after discontinuation or completion of the infusion.
6. Observe the patient for mucositis with sore throat or mouth ulcers followed by a diffuse skin rash. Skin reactions can be life threatening and lead to fatal Stevens-Johnson syndrome or toxic epidermic necrolysis. Patients should be instructed to be observant for signs and symptoms of skin reaction. Patients who develop a sore throat, mucositis should be evaluated and monitored very closely for development of skin reaction, and hospitalized and treated with corticosteroids if indicated. Patients who develop evidence of significant skin rash, oral pharyngeal mucositis that are thought to be related to rituximab should be taken off the study.

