3. PATIENT SELECTION

3.1 Eligibility Criteria

- 3.1.1** Patients must have histologically or cytologically confirmed indolent Non-Hodgkin's Lymphoma (Included in this category are newly diagnosed or relapsed/refractory follicular center lymphomas grade I, II, III, relapsed /refractory marginal zone B-cell lymphoma (nodal and extranodal), relapsed/refractory mantle cell lymphoma).
- 3.1.2** Patients must have measurable disease by CT scan. PET scan evaluations are desirable but not mandatory, so that patients with negative PET scans but measurable disease by CT are eligible.
- 3.1.3** Patients may have had up to four prior chemotherapeutic regimens. Steroids alone and local radiation do not count as regimens (Radiotherapy must have been completed at least 14 days prior to starting vorinostat). Rituxan alone does not count as a regimen, however, Bexxar or Zevalin do. For treated patients, the most recent therapy must have failed to induce a complete response (i.e. there is persistent disease by CT or PET), or there must be disease progression or recurrence after the most recent therapy.
- 3.1.4** Patients may be enrolled who relapse after autologous stem cell transplant if they are at least three months after transplant, and after allogeneic transplant if they are at least six months posttransplant. To be eligible after either type of transplant, patients should have no active related infections (i.e. fungal or viral). In the case of allogeneic transplant relapse, there should be no active acute graft versus host disease (GvHD) of any grade, and no chronic Graft versus Host disease other than mild skin, oral, or ocular GvHD not requiring systemic immunosuppression.
- 3.1.5** Age ≥ 18 years. Because no dosing or adverse event data are currently available on the use of VORINOSTAT in patients < 18 years of age, children are excluded from this study but will be eligible for future pediatric single-agent trials, if applicable.
- 3.1.6** Life expectancy of greater than 3 months.
- 3.1.7** ECOG performance status 2 (Karnofsky $\geq 60\%$; see Appendix A).
- 3.1.8** Patients must have normal organ and marrow function as defined below:
- Absolute Neutrophil Count $\geq 1,000/\text{mcL}$
 - platelets $\geq 100,000/\text{mcL}$
 - total bilirubin within normal institutional limits; patients with elevation of unconjugated bilirubin alone, as in Gilbert's Disease, are eligible.

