3.2 Exclusion Criteria

3.2.1 Patients who have had chemotherapy within 4 weeks, or radiotherapy within 2 weeks or those who have not recovered from adverse events due to agents administered more than 4 weeks earlier are excluded. This does not include use of steroids, which may continue until two days prior to enrollment. Low dose chlorambucil should be stopped two weeks prior to beginning VORINOSTAT. Valproic acid should be stopped at least two weeks prior to enrollment. Nitrosureas and mitomycin should be stopped 6 weeks prior to enrollment.

3.2.2 Patients may not be receiving any other investigational agents.

3.2.3 Patients with known brain metastases are excluded from this clinical trial unless the metastases are controlled after therapy and have not been treated with steroids within the past two months.

3.2.4 History of allergic reactions attributed to compounds of similar chemical or biologic composition to VORINOSTAT.

3.2.5 There must be no plans for the patient to receive concurrent hormonal, biological or radiation therapy.

3.2.6 Uncontrolled intercurrent illness including, but not limited to, ongoing or active infection, symptomatic congestive heart failure, unstable angina pectoris, cardiac arrhythmia, or psychiatric illness/social situations that would limit compliance with study requirements.

3.2.7 Pregnant women are excluded from this study because VORINOSTAT is a HDAC inhibitor agent with the potential for teratogenic or abortifacient effects. Because there is an unknown but potential risk for adverse events in nursing infants secondary to treatment of the mother with VORINOSTAT, breastfeeding should be discontinued if the mother is treated with VORINOSTAT.

3.2.8 HIV-positive patients receiving combination antiretroviral therapy are ineligible because of the potential for pharmacokinetic interactions with VORINOSTAT. In addition, HIV patients not receiving combination antiretroviral therapy are also ineligible as these patients are at increased risk of lethal infections when treated with marrow-suppressive therapy.

3.2.9 Patients with other active malignancies are ineligible for this study.

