4.2 Rituximab Administration

Rituximab will be administered at a dose of 375 mg/m² on day 1 of every cycle, every three weeks. The initial dose rate should be 50 mg/hour IV for the first hour. If no toxicity is seen, the dose rate may be escalated gradually to a maximum of 400 mg/hour. Subsequent doses have required much less infusion time. If the first dose of rituximab is well tolerated, the starting flow rate for subsequent doses is 100 mg/hour, then increased gradually (100 mg/hour increments at 30-minute intervals) not to exceed 400 mg/hour.

Patients may experience transient fever and rigors with infusion. When these occur, the antibody infusion should be temporarily discontinued or slowed. When symptoms improve, the infusion should be resumed, initially at half the previous rate. Following the antibody infusion, the intravenous line should be kept open for medications, as needed. If there are no complications, the intravenous line may be discontinued after one hour of observation.

Oral premedication (acetaminophen and diphenhydramine hydrochloride) may be administered 30 to 60 minutes prior to starting each infusion of rituximab.

Lovenox Administration

Lovenox (enoxaparin) will be administered at a dose of 40 mg subcutaneously daily. Patients will be educated by nursing staff on how to perform daily injections. Administration should be alternated between left and right anterolateral and left and right posterolateral abdominal wall. The whole length of the needle should be introduced into a skin fold held between the thumb and the forefinger. The skin fold should be held throughout the injection.

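### Section 6.2 warns of fatal hepatitis B reactivation under rituximab, but Section 3 and the pre-study calendar require no hepatitis B criterion or test

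*Combined protocol and SAP*

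**What the plan says.** **The warning.** Section 6.2, item 5 of the rituximab side effects, states: "Hepatitis B virus (HBV) reactivation with fulminant hepatitis, hepatic failure, and death has been reported in some patients with hematologic malignancies". It adds: "The majority of patients received rituximab in combination with chemotherapy". It places the median time to diagnosis at "approximately four months after the initiation of rituximab and approximately one month after the last dose".

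**The exposure.** Section 4.2 gives rituximab to all patients "on day 1 of every cycle, every three weeks", so exposure starts on day 1 of cycle 1.

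**The nearest entry criteria.**
- 3.1.4 bars active fungal or viral infection, but only in patients who have had a transplant.
- 3.1.8 requires "total bilirubin within normal institutional limits", with an exception for isolated unconjugated elevation, and allows AST and ALT up to 2.5 times the upper limit of normal.
- 3.2.6 excludes "Uncontrolled intercurrent illness including, but not limited to, ongoing or active infection".

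**The tests.** The pre-study column of the Section 7 calendar includes medical history and serum chemistry. Footnote c lists bilirubin, AST and ALT within that chemistry. No hepatitis B test appears in the column or the footnotes.

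**The setting.** Section 6.2 describes rituximab as commercially available and standard care for this indication. Section 9.2 requires an Eligibility Checklist at registration; the checklist is not in the documents.

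**The concern.** The protocol names a risk of death from one of its two anticancer drugs, gives that drug to everyone, and has no step before the first dose aimed at the patients who carry the risk. Reactivation, the protocol's own term, implies an earlier infection that may be silent at entry. A patient in that state can meet every printed criterion, have a normal baseline chemistry, and be treated exactly as written.

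Other serious rituximab risks in Section 6.2 are matched by an action in its nursing implications: resuscitation equipment for anaphylactoid reactions, prophylaxis for tumor lysis, and removal from study for significant rituximab-related skin or mucosal reactions. Hepatitis B reactivation has no such counterpart.

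What is at stake is patient safety, and consistency between sites in how a known or newly found carrier is handled. The efficacy conclusion is not at stake.

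**Working it through.** There is no stated figure for this point to reproduce. The check is a comparison of the sections that would have to contain a safeguard.

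**1. Eligibility.** Items 3.1.1 to 3.1.10 and 3.2.1 to 3.2.10 make 10 + 10 = 20 numbered criteria. The number naming hepatitis B is 0. Section 3 and the calendar are present in full, so the absence is not a gap in the supplied text.

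**2. What each safeguard would catch.**

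| Safeguard | Would tend to catch | Would not identify |
|---|---|---|
| 3.1.4 | Active viral infection after transplant | Non-transplant patients; inactive carriers |
| 3.1.8 | Overt hepatitis with raised bilirubin, or AST/ALT above 2.5 times the limit | Carriers with normal or mildly raised values |
| 3.2.6 | Uncontrolled active infection that is known | Inactive or unknown carriers |
| Medical history | A carrier who knows it | Unknown carriers; no rule says what follows if one is found |
| Chemistry in weeks 1, 4, 7 and 10 | Liver injury once begun | Carriage before the first dose |
| 5.1 hold for grade 3 or 4 non-hematologic toxicity | Severe injury once begun; it sits under the vorinostat heading and does not name rituximab | Carriage before the first dose |

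The chemistry weeks coincide with the rituximab weeks (1, 4, 7 and 10, 4 of 4), so on-treatment detection is reasonable. Identification before treatment is what is missing.

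**3. Timing after treatment.** Take the earliest complete responder, assuming no delays:
- first response assessment after 3 cycles: 3 × 3 = 9 weeks;
- two more cycles (4.4) are cycles 4 and 5, so the last rituximab dose is on day 1 of cycle 5: 4 × 3 = 12 weeks after the first dose, the start of week 13;
- about one month later is roughly week 17, or about four months from the start.

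That matches the median timing in Section 6.2 and falls after treatment has stopped. Scheduled follow-up for complete responders is then radiologic. The only liver tests printed after treatment are at the off-study visit, whose timing is not given. Because most reported cases also had chemotherapy, this timing may not carry over exactly.

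**4. Effect on the design.** Section 10.1 continues with at least 4 responses in 17 and succeeds with at least 10 in 33. With X1 ~ Bin(17, p) and X2 ~ Bin(16, p):
- P(early stop) = P(X1 ≤ 3) = 0.549 at p = 0.20 (stated 55%);
- P(success) = sum over x1 ≥ 4 of P(X1 = x1) × P(X2 ≥ 10 − x1) = 0.099 at p = 0.20, so P(insufficiently active) = 1 − 0.099 = 0.901 (stated 90%);
- P(success) = 0.888 at p = 0.40 (stated 89%).

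The plan's figures reproduce. Screening acts before entry and changes neither the sample sizes nor the cut-offs, so these figures stand.

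**The case against.** **Sites may already test.** Rituximab is used here as a commercial, standard-care drug, so ordinary practice may include hepatitis B testing. The Eligibility Checklist, the consent template and the registration procedures in Appendix E are also not available to read. This stands as a limit. A reader might infer that patients in this trial go untested; the documents do not support that. They show only that the protocol does not require a test and has no rule for a positive result.

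**Chemotherapy.** Most reported cases had rituximab with chemotherapy, which 4.3.2 bars during the study. This also stands, and risk and timing may differ here. But most is not all, patients may enter after up to four prior regimens or an allogeneic transplant, and Section 6.1 warns that vorinostat combinations could worsen the other agent's known toxicities. The bar does not show the risk to be negligible.

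**Follow-up exists.** Toxicity is assessed on days 1 and 8 of each cycle (4.1), patients are followed to progression or death, and those removed for unacceptable adverse events are followed to resolution or stabilization (4.5). True, but these steps detect harm; they do not screen for it.

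**The HIV exclusion.** A reader might take 3.2.8 as proof that the protocol screens for one virus and ignores another. It does not: the calendar lists no HIV test either. The stated reasons are pharmacokinetic interaction with vorinostat and, for untreated patients, that "these patients are at increased risk of lethal infections when treated with marrow-suppressive therapy", not reactivation by rituximab.

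**Medical knowledge.** The documents do not say which test identifies a carrier or that antiviral cover prevents harm. That is correct. The finding rests on the named risk without a matching step; the choice of panel and management is a clinical assumption for the investigators to confirm.

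**Conclusion.** The gap is real and should be closed. Section 6.2 names a fatal risk of a drug that every patient receives, and neither Section 3 nor the pre-study calendar contains a hepatitis B criterion or test. The existing criteria and chemistry cover active disease and emerging injury, not an inactive or unknown carrier before the first dose.

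Its size cannot be put as a probability. The documents give no carriage or reactivation rate, and none is claimed. The number of patients who could still be tested before their first dose is also unknown. Section 4.3.8 reports five participants with thrombosis, so a reader might infer that 33 − 5 = 28 remain. That is only a ceiling, reached if those five were the only patients enrolled; the true number could be far smaller.

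This is a safety omission, not a statistical error: the endpoint, sample size and error rates are untouched. The conclusion assumes that the unseen checklist and registration documents do not already impose the test. If they do, the remaining change is to bring Section 3 and the calendar into line with them and, if no rule for a positive result exists, to add one.

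**What to change.** 1. Add hepatitis B serology (surface antigen and core antibody) to the pre-study calendar column and the Eligibility Checklist for all patients still to be enrolled, run on the existing pre-study blood draw.
2. Test patients still on rituximab at their next scheduled draw.
3. State in Section 3 that HBV-positive patients are excluded, or are enrolled only with an HBV monitoring and antiviral plan that includes liver tests after the last rituximab dose.

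Cost: amendment wording, one laboratory panel per patient (33 at most if the trial runs to full size), and an occasional ineligible patient. Any HBV-positive patient who is enrolled will also need some post-treatment liver tests, and antiviral treatment where the plan calls for it; these could mean additional blood draws. The screening itself needs no extra visit or invasive procedure.

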6.3 Lovenox

LOVENOX®

Prescribing Information

(enoxaparin sodium injection) for subcutaneous and intravenous use

Rx only

HIGHLIGHTS OF PRESCRIBING INFORMATION

These highlights do not include all the information needed to use Lovenox safely and effectively. See full prescribing information for Lovenox.

Lovenox® (enoxaparin sodium injection) for subcutaneous and intravenous use
Initial U.S. Approval: 1993

WARNING: SPINAL/EPIDURAL HEMATOMA

Epidural or spinal hematomas may occur in patients who are anticoagulated with low molecular weight heparins (LMWH) or heparinoids and are receiving neuraxial anesthesia or undergoing spinal puncture. These hematomas may result in long-term or permanent paralysis. Consider these risks when scheduling patients for spinal procedures. Factors that can increase the risk of developing epidural or spinal hematomas in these patients include:

- Use of indwelling epidural catheters
- Concomitant use of other drugs that affect hemostasis, such as non-steroidal anti-inflammatory drugs (NSAIDs), platelet inhibitors, other anticoagulants
- A history of traumatic or repeated epidural or spinal punctures
- A history of spinal deformity or spinal surgery.

Monitor patients frequently for signs and symptoms of neurological impairment. If neurological compromise is noted, urgent treatment is necessary.

Consider the benefits and risks before neuraxial intervention in patients anticoagulated or to be anticoagulated for thromboprophylaxis [see [Warnings and Precautions \(5.1\)](#) and [Drug Interactions \(7\)](#)].

RECENT MAJOR CHANGES

Administration ([2.4](#))

(04/2011)

INDICATIONS AND USAGE

Lovenox is a low molecular weight heparin [LMWH] indicated for:

- Prophylaxis of deep vein thrombosis (DVT) in abdominal surgery, hip replacement surgery, knee replacement surgery, or medical patients with severely restricted mobility during acute illness ([1.1](#))
- Inpatient treatment of acute DVT with or without pulmonary embolism ([1.2](#))
- Outpatient treatment of acute DVT without pulmonary embolism. ([1.2](#))
- Prophylaxis of ischemic complications of unstable angina and non-Q-wave myocardial infarction [MI] ([1.3](#))
- Treatment of acute ST-segment elevation myocardial infarction [STEMI] managed medically or with subsequent percutaneous coronary intervention [PCI] ([1.4](#))

DOSAGE AND ADMINISTRATION

Indication	Dose
DVT prophylaxis in abdominal surgery	40 mg SC once daily
DVT prophylaxis in knee replacement surgery	30 mg SC every 12 hours
DVT prophylaxis in hip replacement surgery	30 mg SC every 12 hours or 40 mg SC once daily
DVT prophylaxis in medical patients	40 mg SC once daily
Inpatient treatment of acute DVT with or without pulmonary embolism	1 mg/kg SC every 12 hours or 1.5 mg/kg SC once daily *
Outpatient treatment of acute DVT without pulmonary embolism	1 mg/kg SC every 12 hours *
Unstable angina and non-Q-wave MI	1 mg/kg SC every 12 hours (with aspirin)
Acute STEMI in patients <75 years of age [For dosing in subsequent PCI, see Dosage and Administration (2.1)]	30 mg single IV bolus plus a 1 mg/kg SC dose followed by 1 mg/kg SC every 12 hours (with aspirin)
Acute STEMI in patients ≥75 years of age	0.75 mg/kg SC every 12 hours (no bolus) (with aspirin)

- See recommended durations for Lovenox therapy ([2.1](#))
- *See recommendations regarding transitioning to warfarin therapy ([2.1](#))
- Adjust the dose for patients with severe renal impairment ([2.2](#), [8.7](#))

DOSAGE FORMS AND STRENGTHS

100 mg/mL concentration ([3.1](#)):

- Prefilled syringes: 30 mg/0.3 mL, 40 mg/0.4 mL
- Graduated prefilled syringes: 60 mg/0.6 mL, 80 mg/0.8 mL, 100 mg/1 mL
- Multiple-dose vial: 300 mg/3 mL

150 mg/mL concentration ([3.2](#)):

- Graduated prefilled syringes: 120 mg/0.8 mL, 150 mg/1 mL

CONTRAINDICATIONS

- Active major bleeding ([4](#))
- Thrombocytopenia with a positive in vitro test for anti-platelet antibody in the presence of enoxaparin sodium ([4](#))
- Hypersensitivity to enoxaparin sodium ([4](#))
- Hypersensitivity to heparin or pork products ([4](#))
- Hypersensitivity to benzyl alcohol [for multi-dose formulation only] ([4](#))

WARNINGS AND PRECAUTIONS

- Increased risk of hemorrhage: Use with caution in patients at risk ([5.1](#))
- Percutaneous coronary revascularization: Obtain hemostasis at the puncture site before sheath removal ([5.2](#))
- Concomitant medical conditions: Use with caution in patients with bleeding diathesis, uncontrolled arterial hypertension or history of recent gastrointestinal ulceration, diabetic retinopathy, renal dysfunction, or hemorrhage ([5.3](#))
- History of heparin-induced thrombocytopenia: Use with caution ([5.4](#))
- Thrombocytopenia: Monitor thrombocytopenia closely ([5.5](#))
- Interchangeability with other heparins: Do not exchange with heparin or other LMWHs ([5.6](#))
- Pregnant women with mechanical prosthetic heart valves and their fetuses, may be at increased risk and may need more frequent monitoring and dosage adjustment ([5.7](#))

ADVERSE REACTIONS

Most common adverse reactions (>1%) were bleeding, anemia, thrombocytopenia, elevation of serum aminotransferase, diarrhea, and nausea ([6.1](#))

DRUG INTERACTIONS

Discontinue agents which may enhance hemorrhage risk prior to initiation of Lovenox or conduct close clinical and laboratory monitoring ([5.9](#), [7](#))

USE IN SPECIFIC POPULATIONS

- Severe Renal Impairment: Adjust dose for patients with creatinine clearance <30mL/min ([2.2](#), [8.7](#))
- Geriatric Patients: Monitor for increased risk of bleeding ([8.5](#))
- Patients with mechanical heart valves: Not adequately studied ([8.6](#))
- Hepatic Impairment: Use with caution. ([8.8](#))
- Low-Weight Patients: Observe for signs of bleeding ([8.9](#))

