4.3.8 Anticoagulation prophylaxis

Patient will need to take Lovenox 40 mg subcutaneously daily when patients are getting active treatment with vorinostat and rituxan. Five research participants on this study have developed either pulmonary embolism or deep vein thrombosis. These have been without symptoms and found on CT scans. Lovenox (40 mg) subcutaneously will be taken starting from Cycle 1 Day 1 of study to prevent pulmonary embolus and deep vein thrombosis. Lovenox will continue for at least 28 days status post last dose of vorinostat or rituximab. For patients with creatinine clearance less than 30 ml/min, lovenox dose will be 30 mg subcutaneously daily. Elderly patients with creatinine clearance less than 50 ml/min should also be dosed at 30 mg subcutaneously daily.

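### Daily enoxaparin is required from Cycle 1 Day 1, but no eligibility or dosing rule carries over the hypersensitivity contraindications printed in Section 6.3

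*Combined protocol and SAP*

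**What the plan says.** The Lovenox Administration paragraph under Section 4.2 states: "Lovenox (enoxaparin) will be administered at a dose of 40 mg subcutaneously daily". Section 4.3.8 fixes the start: "Lovenox (40 mg) subcutaneously will be taken starting from Cycle 1 Day 1 of study". It continues the drug for at least 28 days after the last vorinostat or rituximab dose. The schema and the study calendar also list it.

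The reason is given in Section 4.3.8: "Five research participants on this study have developed either pulmonary embolism or deep vein thrombosis".

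The exceptions are few:

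- Section 3.2.10: patients already on Coumadin or Lovenox need no additional study injections.
- Section 4.3.8: the dose is 30 mg when creatinine clearance is below 30 ml/min, or below 50 ml/min in elderly patients.
- Section 5.1, Lovenox part: the drug is held when platelets fall below 50K, until they recover.

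Section 6.3 reproduces the label highlights. Their contraindications include "Hypersensitivity to enoxaparin sodium" and "Hypersensitivity to heparin or pork products". The only allergy exclusion, 3.2.4, concerns compounds resembling vorinostat. Section 9.2 rules out waivers and treatment deviations except for the delays described in 5.1 and 5.2.

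**The concern.** The dosing rule and the contraindication list sit in the same protocol and disagree. Applied literally, the criteria admit a patient with a known heparin, enoxaparin or pork allergy who is not on Coumadin. The dosing sections then call for a drug that Section 6.3 says that patient should not receive. A site that rightly withholds it departs from 4.3.8, has no named alternative, and finds no allowance for the omission in 9.2.

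The same gap affects a patient who first reacts on study. No rule stops enoxaparin and leaves vorinostat and rituximab running, so a patient could lose study therapy because of a prophylactic drug.

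This is a matter of patient safety and consistent conduct. It does not affect the response-rate analysis.

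**Working it through.** The protocol gives no figure on this point, so the check is to read the rules against the contraindications.

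**Step 1. Eligibility.** There are 10 criteria in 3.1 (3.1.1 to 3.1.10) and 10 in 3.2 (3.2.1 to 3.2.10), so 10 + 10 = 20. None names allergy to enoxaparin, heparin or pork. Criterion 3.2.4 is limited to vorinostat-like compounds. Criterion 3.2.6 covers uncontrolled intercurrent illness, and a drug allergy is not naturally read as that.

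**Step 2. The five printed contraindications against the rules.**

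| Section 6.3 contraindication | Where the rules deal with it |
|---|---|
| Active major bleeding | Open wording of 3.2.6 |
| "Thrombocytopenia with a positive in vitro test for anti-platelet antibody in the presence of enoxaparin sodium" | Largely, though not by name: 3.2.6, the entry platelet minimum of 100,000, and the hold below 50K (which lasts only until recovery) |
| Enoxaparin hypersensitivity | Nowhere |
| Heparin or pork hypersensitivity | Nowhere |
| Benzyl alcohol hypersensitivity | Concerns the multi-dose formulation only. Section 6.3 lists single-dose forms for both protocol doses: "Prefilled syringes: 30 mg/0.3 mL, 40 mg/0.4 mL" |

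Wholly or largely handled: 3. Clearly uncovered: 5 − 3 = 2.

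**Step 3. A reaction first seen on study.**

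- The grade 3 or 4 non-hematologic hold in 5.1 stands under the vorinostat heading. It restarts treatment at 100 mg daily less, which is a vorinostat step, and recurrence at grade 3 or greater takes the patient off study.
- A grade 1 or 2 allergic reaction does not reach that hold at all.
- Section 4.4 ends treatment as a whole for unacceptable adverse events.
- The Lovenox part of 5.1 deals only with platelets.

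None of these stops enoxaparin alone.

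**Step 4. Effect on the efficacy design.** Section 10.1 uses 17 then 33 patients, continues at 4 or more responses and succeeds at 10 or more. None of these depends on enoxaparin. Section 10.5.1 keeps patients with incorrect drug administration in the response analysis, so omitting enoxaparin would not remove a patient from it.

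**Step 5. Frequency.** The documents give no prevalence of enoxaparin, heparin or pork allergy, so no probability or expected count is computed.

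**The case against.** The strongest reply is that Section 6.3 is part of this protocol. It lists these allergies under contraindications and directs the reader onward: "See full prescribing information for Lovenox". Medical history is a required pre-study item. The bar on deviations in 9.2 closes a section on registration, while 10.5.1 plainly expects that some treatment deviations will occur. Section 4.4 leaves room for the investigator's judgment. On this view only a cross-reference is missing.

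Much of that stands. A reader might infer that the protocol compels sites to inject a contraindicated drug. The documents do not support that: read as a whole, they tell the investigator when enoxaparin should not be used, and a competent site would probably act on it. What remains is that 6.3 is reproduced label text tied to neither eligibility nor dosing, that 4.4 ends all treatment rather than enoxaparin alone, and that no alternative prophylaxis is named.

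It can also be said that crediting 3.2.6 for bleeding but not for allergy applies two standards. The count of 2 out of 5 does rest on that judgment. It is defensible because active major bleeding is an uncontrolled illness in the ordinary sense and a history of drug allergy is not.

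A reader might also try to size the problem from the five thromboembolic events and the maximum of 33 patients. Those numbers say nothing about allergy, and the documents do not state enrolment when prophylaxis was introduced.

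Finally, the Eligibility Checklist is not reproduced and the consent pages were removed, so allergy screening there cannot be ruled out.

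**Conclusion.** The point holds as a low-frequency safety gap. Two of the five contraindications printed in Section 6.3, hypersensitivity to enoxaparin and hypersensitivity to heparin or pork products, reach neither the eligibility criteria nor the enoxaparin dosing rules. No rule stops enoxaparin alone after an allergic reaction. The stated requirement and the stated contraindications therefore conflict, and the general wording elsewhere does not resolve it.

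The size is modest. Few patients are likely to be affected, though the documents give no prevalence to show how many, and clinicians would probably catch most cases. The two-stage design, its decision rule and the response analysis are unaffected.

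A reader might infer that an entry exclusion is essential. It is not, once an omission rule exists. An exclusion also could not help a patient who first reacts on study, or one already enrolled when enoxaparin was introduced. That there are such patients is an inference from Section 4.3.8, which reports on-study events beside the prophylaxis rule.

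The conclusion assumes that the unreproduced checklist does not already screen for these allergies.

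**What to change.** Add one sentence to 4.3.8 and to the Lovenox part of 5.1:

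> Enoxaparin is not given, or is permanently stopped, if a contraindication listed in Section 6.3 is present or develops. The investigator chooses alternative prophylaxis, and this is not a deviation under Section 9.2.

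The choice of alternative needs a short note. Section 6.3 cautions against exchanging enoxaparin with heparin or other low molecular weight heparins. If warfarin is used, INR should be monitored: Section 6.1 lists INR change among vorinostat adverse events, and Appendix C lists warfarin as a CYP2C8/9 substrate.

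If the clinical team does not accept treatment without enoxaparin, the alternative is an exclusion in 3.2 for known enoxaparin, heparin or pork hypersensitivity in patients not otherwise anticoagulated. The stopping rule for reactions on study would still be needed.

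The cost is a sentence or two of text. Prophylaxis would not be uniform in the few exempted patients or, if the exclusion is used, slightly fewer patients would be eligible. Sample size, decision rules and analysis do not change.
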